# Feasibility

The principal investigator has long term experience in carrying on and coordinating epidemiological studies, including small-scale dietary intervention studies (22, 29, 30). The European Institute of Oncology has long term experience in chemoprevention studies. The Milan National Cancer Institute is fully equipped with facilities for kitchen courses, dedicated cafeteria, gym facilities. The Palermo oncology center has access to kitchen facilities in a nearby technical institute and has already carried out a dietary intervention study with very high compliance. The above institutions treat, respectively, about 3,000, 1,000 and 200 BC patients per year.

### **Control of potential biases**

Selection bias: the randomization will be carried out blindly, without any possibility of changing the allocation, within strata of age, date of diagnosis, treatment allocation (depending on stage and hormone receptor status) and number of positive axillary nodes at diagnosis (none, 1-3, 3 or more). Performance bias: patients will be recruited after the main treatments have been planned or delivered. In no case the allocation to the intervention or control group or the compliance will affect treatment.

Measurement bias: patients and researchers cannot be blinded, but the ascertainment of outcome will be carried out by clinicians that are not involved in the study. Attrition bias: Based on previous studies we expect a fairly high compliance in the intervention

group (>90%) but also some modification in the control group. After the main analysis by intention to treat, therefore, secondary analyses will be carried out by compliance score. Milestones and timing:

 $1^{st}$ )

3rd Month:  $2^{nd}$ ) 12th Month: 16th 3rd) Month:

testosterone by 10% or more and serum glucose and insulin by 5% or more in at least 50% of participants.

Operative study protocol and information system

Recruitment of at least 300 patients in the first year.

Compliance evaluation. The aim is to decrease serum cholesterol and

4th) 24th Month: Test of follow-up procedures and comparison of observed and expected number of recurrences

5th) 35th Month: First outcome analysis

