We now propose a randomized dietary and physical activity intervention trial to reduce BC recurrences (local, distant, or second BC) in BC patients at high risk because of high serum testosterone (>0.4 ng/ml), or insulin (>50 pmol/L), or the presence of metabolic syndrome. In these patients the estimated 5-year cumulative recurrence rate is 30%. Participants will be recruited through hospitals, patients' associations, and the media. We plan to recruit 1,200 patients and to randomize them in two groups: 600 shall receive standard recommendation for healthy lifestyle without, however, any active support; 600 shall receive a combination of individual and group contacts over the course of one year, including kitchen courses, gym and dance classes, common meals and reinforcing meetings, with emphasis on a comprehensive dietary change including low saturated fat and low refined carbohydrates, and high whole grain cereals and pulses consumption. Compliance will be monitored through weight change and plasma glucose, triglycerides, cholesterol and testosterone.

The main analysis will be by intention to treat. Under the hypothesis of reducing recurrence rate by 25% or 33% the statistical power of the study is 80% or, respectively, 90%, (P<0.05, 5-year follow-up).

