#### **Statistical power**

The survival of BC patients in Italy is dramatically increasing: 5-year relative survival increased from 80.6% for patients diagnosed in the early 1990s (Berrino et al, EUROCARE-3) (45) to 85.6% for patients diagnosed in the early 2000s (EUROCARE-4, unpublished). For these patients the estimated relapse free survival is 81.9 (EUROCARE high resolution study, unpublished). Such a survival improvement is accompanied by a postponement of the incidence of relapse (table 4). *Table 4. incidence rate of local + distant recurrences (EUROCARE, unpublished)* 

Follow-up year	relapse rate %	95% confidence interval
1 st	3.4	2.0 -5.8
$2^{nd}$	4.7	3.0-7.5
3 rd	5.1	3.2-8.1
4 th	4.7	2.9-7.8
5 th	2.1	0.9-4.6
$6^{\text{th}}$ to $8^{\text{th}}$	2.2	1.4-3.0

Based on EUROCARE data we estimate that the 5-year distant recurrences plus second ipsilateral or contralateral BC for patients recruited in the first few years after diagnosis will be about 20%. In the subgroup of patients selected on the basis of high insulin and/or testosterone levels (50% of cases with RR of the order of 3), we estimate that about 30% of patients will develop a recurrence or a second primary BC within 5-year follow-up: 360 cases out of 1200. Considering that the WINS randomized study obtained a 24% reduction of recurrence rate changing a single dietary factor (total fat) (39), and that observational studies suggested that a moderate physical activity may reduce recurrence rate by over 40% (28), we hypothesize that a comprehensive dietary intervention plus physical activity will reduce BC recurrence rate by 33% or more, but we consider also a more prudent estimate of 25% reduction.

The following table gives the number of patients (per arm) that we should recruit in order to have 90% or 80% power to detect a significant difference with  $\alpha < 0.05$ , two sided, or one sided ( $\alpha < 0.10$ ).

Power (1-β)	0.9	0.9	0.8	0.8
α	0.05	0.10	0.05	0.10
33% reduction	412	339	313	251
25% reduction	748	614	566	451

Our aim is to recruit 1,200 high risk patients in order to have 600 patients per arm, which shall guarantee 80% chance of getting a significant difference also with 25% reduction, and allowing for 90% compliance in the intervention group and 10% contamination of the control group.

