### Statistical analysis

We shall first assess the baseline association between androgens, insulin, and several measures of adiposity including body mass index, waist circumference and (in a sample of cases) percentage body fat, with Spearman correlation coefficients. We shall then compare the change in food consumption, body weight, and geometric means of hormone end points from baseline to 12 months in the intervention and control group.

The main analysis of the intervention effect on the incidence of recurrences will be by intention to treat, i.e. based on assigned treatment at the time of randomization, regardless of adherence. As a secondary analysis we shall assess the effect by change in body weight and biomarkers. We shall compute total survival, disease free survival and relapse free survival.

Hazard ratios and confidence intervals will be computed by the Cox proportional hazard model, with standard clinical-pathological prognostic covariates as potential confounders. Separate analyses will be carried out by ER, PR and erbB2 status. Interim analyses will be carried out as soon as the total follow-up person-years reach 2,500 (corresponding to  $\alpha$  =0.10 and  $\beta$ = 0.20 for a 33% reduction of recurrence rate).

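### The analysis by compliance score offered as the remedy for non-compliance and control-arm change is an observational comparison; a randomisation-based estimate should take that role

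*Combined protocol and SAP*

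**What the plan says.** Under Control of potential biases (attrition bias), the combined protocol and SAP expects compliance above 90% in the intervention arm and some change among controls, and concludes: "After the main analysis by intention to treat, therefore, secondary analyses will be carried out by compliance score". The word 'therefore' makes the score analysis the stated answer to dilution.

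The Compliance section builds the score from whether each monitored biomarker rose or fell after one year of intervention. It gives no cut-off and no comparison groups. The Statistical analysis section adds: "As a secondary analysis we shall assess the effect by change in body weight and biomarkers". The only adjustment it names is for the usual clinical and pathological prognostic factors, in a Cox model.

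The sample size is described as "allowing for 90% compliance in the intervention group and 10% contamination of the control group". Intention to treat is the main analysis throughout. No randomisation-based estimate of the effect of uptake is planned, no starting point for follow-up in the score analysis is given, and nothing limits how its result may be interpreted.

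**The concern.** Women whose weight, lipids, insulin and testosterone improve over a year are not a random subset of those assigned. They may differ in fitness, tolerance of adjuvant therapy and prognosis, and early unrecognised disease can itself change weight and lipids. Selection into the trial on high marker values adds regression to the mean, which also sorts women by later change. The protocol itself treats these markers as strongly prognostic, with a relative risk of about 3 under Statistical power. A recurrence difference between score groups therefore mixes any effect of the intervention with the prognosis of the women who improve.

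At stake is how a weak or null main result would be read. Suppose a 25% reduction is real and is diluted by 90% compliance and 10% contamination. The 5-year risks become 29.25% and 23.25%, and power at 600 per arm is about 66% (two-proportion formula without continuity correction). A non-significant main result is then quite possible, and an analysis presented as correcting for dilution would be a natural fallback.

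**Working it through.** **Inputs from the plan.**
- Event risk: "we estimate that about 30% of patients will develop a recurrence or a second primary BC within 5-year follow-up: 360 cases out of 1200", that is, 30% overall.
- Target: the intervention "will reduce BC recurrence rate by 33% or more, but we consider also a more prudent estimate of 25% reduction", that is, 30% to 20% or 30% to 22.5%.
- Two-sided alpha 0.05, 600 per arm, 90% compliance and 10% contamination.

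**Plan's own figure.** For 30% versus 22.5% at 80% power, the mean risk is 0.2625.
- n = [1.96·√(2 × 0.2625 × 0.7375) + 0.842·√(0.30 × 0.70 + 0.225 × 0.775)]² / 0.075² = 540 per arm after rounding up.
- The continuity correction, (n/4)·[1 + √(1 + 4/(0.075n))]², gives 566, as tabulated. The other seven cells also reproduce, taking the 33% reduction as 30% to 20%.

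**Assumption that the plan does not supply.** Let k be the ratio of 5-year risk in low-score to high-score women within an arm when the intervention does nothing. Overall risk is held at 30% in each arm. If a share q scores high, risk in the high group is 0.30 / (q + (1 − q)k), and risk in the low group is k times that.

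**High versus low score, q = 0.5.** The milestone of reaching biomarker targets in at least half of participants makes a middle split plausible, but the plan does not specify one.
- k = 1.33: 0.30 / 1.165 = 25.8% versus 34.2%, RR 0.75.
- k = 1.5: 0.30 / 1.25 = 24% versus 36%, RR 0.67.

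**Planned 90%/10% split, k = 1.5.**
- Intervention arm: compliant 0.30 / 1.05 = 28.57%; non-compliant 42.86%.
- Control arm: changed 0.30 / 1.45 = 20.69%; unchanged 31.03%.
- Compliant intervention versus all controls: 28.57 / 30 = 0.95.
- Compliant intervention versus unchanged controls: 28.57 / 31.03 = 0.92.
- Pooled as treated: (0.9 × 28.57 + 0.1 × 20.69) / (0.1 × 42.86 + 0.9 × 31.03) = 27.78 / 32.22 = 0.86.
- The pooled contrast reaches 0.75 only for k between 2 and 2.5.

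**Chance of a significant false contrast.** The score needs the one-year sample, so earlier recurrences generally have no score. The five yearly relapse rates in Table 4 sum to 20.0, of which year 1 contributes 3.4. That leaves 360 × (1 − 3.4/20.0) ≈ 299 events. This is approximate, because the table's clock may not be time since randomisation. With an assumed hazard ratio h, P(significant) = Φ(|ln h|·√(D·q·(1 − q)) − 1.96), with D = 299:

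| h | q = 0.5 | q = 0.7 |
|---|---|---|
| 0.8 | Φ(1.93 − 1.96) = 49% | Φ(1.77 − 1.96) = 42% |
| 0.7 | Φ(3.08 − 1.96) = 87% | Φ(2.83 − 1.96) = 81% |

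Within the intervention arm alone (about 150 events, q = 0.5) the figures are 28% and 59%. Here h is an input; only the probability is calculated.

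**Randomisation-based alternative.** The complier-average effect is the difference in 5-year risk between arms divided by the difference in uptake.
- No effect: 0 / (0.90 − 0.10) = 0, whatever the value of k.
- True 25% reduction, with everyone at 30% baseline risk: the arms have 0.30 − 0.1 × 0.075 = 29.25% and 0.30 − 0.9 × 0.075 = 23.25%, so 0.060 / 0.80 = 0.075.

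**The case against.** Four points on the other side carry weight.

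- **Position in the plan.** Intention to treat is primary, and the score analysis is explicitly secondary. A reader might infer that the trial's main conclusion is compromised, or that the plan means to claim efficacy from the score. The documents support neither. What stands is that an analysis listed as bias control does not control the bias.
- **Size.** A reader might infer that a false benefit as large as the design target is to be expected. That needs a high-versus-low split or a large prognostic difference. At the plan's own 90%/10% split the distortion is modest, and an assumed hazard ratio of 0.8 falls short of the 25% target.
- **Mitigation.** The Cox model adjusts for prognostic factors, biomarkers are compared within the same treatment phase, and women with signs suggesting recurrence are not eligible. These may remove part of the bias, and the figures above are unadjusted. They do not reach the other traits of women who improve.
- **The alternative.** The complier-average estimate returns 7.5 points only if compliers share the 30% baseline risk; otherwise it is an effect specific to compliers. Assignment also brings group support, common meals and regular weighing, and partial change among women classed as non-adherent strains a yes/no indicator. Self-report in an unblinded trial may distort the size of the estimate. At 90%/10% it is close to a rescaled intention-to-treat result and cannot rescue a null one.

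A reader might also infer that the analysis by weight and biomarker change should be dropped. It can serve the secondary aim on intermediate factors and needs labelling, not removal.

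**Conclusion.** The concern holds in limited form. The stated remedy for non-compliance and control-arm change compares groups formed after randomisation, so it can show a benefit when there is none. Its size cannot be fixed from the documents, because the contrast is undefined and the prognostic difference is an assumption. A modest difference matches the 25-33% target under a 50/50 high-versus-low split, whereas the same 1.5-fold difference produces a 5-14% apparent reduction under the planned split. The harm is to the interpretation of a secondary analysis. The correction is cheap and worth making before outcome data are seen.

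**What to change.** - **Control of potential biases:** name a complier-average causal effect on 5-year recurrence risk as the secondary analysis that allows for non-compliance and contamination. Use randomised arm as the instrument and keep all randomised women. Define a yes/no adherence indicator measured the same way in both arms; the yearly diet and activity questionnaire already goes to both. Give a rule for women whose event or withdrawal precedes it.
- **State the assumptions:** assignment affects recurrence only through uptake, no woman takes up the programme only if assigned to control, and self-report without blinding may distort the size of the estimate.
- **Analyses by score, weight change and biomarker change:** keep them as exploratory prognostic associations. Define the groups and cut-offs in advance, start follow-up at the one-year sample, and state that they do not support an efficacy conclusion.

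The cost is SAP wording and a little analysis work, with no new data collection. The interval is wider than that of the score comparison; relative to the intention-to-treat risk difference it widens by about 1 / 0.80 = 1.25 at the planned uptake.
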